#### **5.1.1.1.5 Definition of Baseline values**

*Baseline is defined as the last nonmissing pretreatment measurement. Therefore, data from the Screening Visit (if available) will be used as Baseline values if data are missing at Week 0. No other data will be considered for Baseline.*

#### **5.1.1.2 Protocol Deviations**

Important protocol deviations are deviations from the protocol which potentially could have a meaningful impact on study conduct or on the primary PK outcome for an individual study participant. PK samples outside the protocol windows, missing doses or delayed doses potentially impacting PK, will be reviewed. PK sampling protocol deviations will not automatically cause their exclusion from the PKS set. The table of summary PK statistics and geometric mean PK concentration-time figure will be presented with and without those PK samples determined to be protocol deviations.

The criteria for identifying important protocol deviations will be defined within the appropriate protocol-specific document at study start. Important protocol deviations will be reviewed as part of the ongoing data cleaning process.

Furthermore, overall trends in protocol deviations will be discussed at the Data Evaluation Meeting. Through this data cleaning and evaluation process, all decisions regarding important protocol deviations and exclusions from analysis populations will be made. Important protocol deviations including those that lead to exclusion from the analysis sets will be identified and documented prior to database lock.

All tabulations and listing of protocol deviations will be performed for all study participants.

#### **5.1.1.3 Treatment assignment and treatment groups**

This is open label and one arm study; the case of treatment misallocation will be not applicable.

#### **5.1.1.4 Center pooling strategy**

The data from all centers will be pooled together for analyses.

#### **5.1.1.5 Coding dictionaries**

All AEs and medical history will be coded for analysis according to the Medical Dictionary for Regulatory Activities (MedDRA)® coding dictionary, using the MedDRA version 23.1. Prior and

concomitant medications will be coded for analysis using the version Sep/2020 B3 update of the World Health Organization Drug dictionary (WHO-DD). Medical procedures will not be coded.

### 5.1.1.6 Multicenter studies

The data from all centers will be pooled together for analyses. Individual center results will not be displayed.

## 5.2 Participant Dispositions

The following summary outputs will be presented.

- **Reasons for screen failures** will be summarized using the All Study Participants (ASP), including rescreened study participants.
- **Disposition of study participants screened** will be summarized using the ASP for overall and by site. In this summary, the site number, principal investigator name, first participant in date, last participant out date, number of study participants screened will be captured by each analysis set (SS).
- **Disposition and Discontinuation Reasons** using the SS will contain the number and percentage of study participants by loading dose phase and maintenance phase.
- **Discontinuation due to AEs** will be summarized for following type of AEs using the SS:
  - AE, serious fatal,
  - AE, non-fatal,
  - Other (AE, non-serious fatal).
- **Impact of COVID-19** using the ASP will summarize number and percentage of participants in each impact category by visit.

The number of study participants who started into the study and study participants who completed or prematurely discontinued the study, as well as the reason for discontinuation, will be presented by CZP loading dose(400 mg) and CZP maintenance dose (200 mg) for SS. A participant who completed the whole study is defined as a participant who completed the last scheduled Safety-Follow-Up Visit, ie, the participant will be regarded as a completer if the safety-follow-up (Visit 16, 70 days after last IMP through SFU visit) visit was completed. The number and percentage of study participants who discontinued due to AEs will be separately summarized based on the SS.

Screen failure reasons will be summarized based on All Study Participants (ASP). A listing of study participants who did not meet study eligibility criteria (including glossary) will also be presented based on All Study Participants (ASP).

In addition, the following listings will be presented for all study participants :

- Study participant disposition (ASP)
- Study discontinuation (ASP)
- Visit dates (ASP)
- Subject analysis sets (ASP )

Study participant disposition will be listed for all study participants based on the All Study Participants (ASP), and will include the date of informed consent, date and time of dosing, date of premature termination and primary reason (if applicable), and date of final contact.

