1.3 Schedule of Activities

Procedure	Screening	Baseline	Treatment Period													SFU/ EDV
	V1	V2	V3	V4	V5	V6	V7	V8	PK profile				V13	V14	V15	V16
	D-28/ W-4	D0	D7/ W1	D14/ W2	D28/ W4	D42/ W6	D56/ W8	D70/ W10	D72/ W10	D75/ W10	D77/ W11	D80/ W11	D84/ W12	D126/ W18	D168/ W24	70 days after last IMP
Visit window ^a			±1 day	±1 day	±2 days	±2 days	±2 day	±1 day	±6 hrs	±6 hrs	±6 hrs	±6 hrs	±6 hrs	±2 days	±2 days	±7 day
Location ^b	Clinic	Clinic	Clinic	Home	Home	Clinic	Home	Home	Home	Home	Home	Home	Clinic	Home	Clinic	Clinic
Informed consent	X															
Study participant card	X															
Verification of inclusion/exclusion criteria	X															
Demography	X															
General medical/procedure history	X															
Physical examination	X															X
Body weight/height	X															
Vital signs	X															X
Pregnancy test ^c	X												X			X
Laboratory assessments	X												X			X
12-lead ECG ^d	X															
TB questionnaire	X												X		X	

Procedure	Screening	Baseline	Treatment Period													SFU/ EDV
	V1	V2	V3	V4	V5	V6	V7	V8	PK profile				V13	V14	V15	V16
	D-28/ W-4	D0	D7/ W1	D14/ W2	D28/ W4	D42/ W6	D56/ W8	D70/ W10	D72/ W10	D75/ W10	D77/ W11	D80/ W11	D84/ W12	D126/ W18	D168/ W24	70 days after last IMP
Visit window ^a			±1 day	±1 day	±2 days	±2 days	±2 day	±1 day	±6 hrs	±6 hrs	±6 hrs	±6 hrs	±6 hrs	±2 days	±2 days	±7 day
Location ^b	Clinic	Clinic	Clinic	Home	Home	Clinic	Home	Home	Home	Home	Home	Home	Clinic	Home	Clinic	Clinic
TB screening (IGRA)	X															
Adverse event review	X	X	X	X	X	X	X	X	X	X	X	X	X	X	X	X
Prior and Concomitant medication review	X	X	X	X	X	X	X	X					X		X	X
IMP administration ^e		X (site)		X (nurse)	X (nurse)	X (site)	X (nurse)	X (nurse)					X (site)	X (nurse or self)	X (site)	
IMP dispensing/ IXRS		X				X							X			
IMP return						X							X		X	
CZP plasma concentration ^{f, g}		X	X	X		X		X	X	X	X	X	X	X	X	
Anti-CZP antibody sampling ^f		X				X							X		X	X
RAPID3 testing ^f		X											X			

CZP=certolizumab pegol; D=day; ECG=electrocardiogram; EDV=Early Discontinuation Visit; hrs=hours; IGRA=Interferon-gamma release assay; IMP=investigational medicinal product; Q2W=every 2 weeks; PK=pharmacokinetic(s); RAPID3=Routine Assessment of Patient Index Data; SFU=Safety Follow-up; TB=tuberculosis; V=Visit; W=week

^a Visit days may take place within a window relative to the Visit Day.

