4.4 End of study definition

A participant is considered to have completed the study if he/she has completed all portions (Screening, Baseline Visit, Treatment Period [through Week 24], and SFU) of the study.

Following investigational medicinal product (IMP) administration at Week 24, participants may transition to treatment with commercial CZP in consultation with their health care professional. The SFU Visit will be conducted 70 days post last administration of IMP.

The end of the study is defined as the date of the last visit of the last participant in the study.

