8.3.5 Pregnancy

Details of all pregnancies in female participants and, if indicated, female partners of male participants will be collected after the start of study treatment and until SFU Visit.

If a pregnancy is reported, the Investigator must inform the Sponsor within 24 hours of learning of the pregnancy and should follow the procedures outlined in Appendix 4 (Section 10.4).

The participant should be withdrawn from the study as soon as pregnancy is known (by positive pregnancy test), and the following should be completed:

- The participant should immediately stop the intake of the study medication.
- The participant should return for an Early Discontinuation Visit.
- An SFU Visit should be scheduled 70 days after the participant has discontinued her study medication.
- The participant should complete a Pregnancy Outcome Form per UCB Standard Operating Procedures.

Abnormal pregnancy outcomes (eg, spontaneous abortion, fetal death, stillbirth, congenital anomalies, ectopic pregnancy) are considered SAEs.

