
 Monitor the participant until liver chemistry test abnormalities resolve, stabilize, or return to baseline (see MONITORING). Do not restart/rechallenge participant with study medication unless allowed per protocol and UCB approval is granted. If restart/rechallenge not allowed per protocol or not granted, permanently discontinue study medication and continue participant in the study for any protocol-specified follow-up assessments. Consider the need for a toxicology screening. 
MONITORING:
 
For bilirubin or INR criteria
 
 Repeat liver chemistry tests (include ALT, aspartate transaminase [AST], alkaline phosphatase, bilirubin) and perform liver event follow-up assessments within 24 hours. Monitor participant twice weekly until liver chemistry test abnormalities resolve, stabilize, or return to baseline. A specialist or hepatology consultation is recommended. 
For all other criteria
 
 Repeat liver chemistry tests (include ALT, AST, alkaline phosphatase, bilirubin) and perform liver chemistry follow-up assessments within 24 to 72 hours. Monitor participants weekly until liver chemistry abnormalities resolve, stabilize, or return to baseline. 	
 quantitative hepatitis B deoxyribonucleic acid (DNA), and hepatitis delta antibody.^e Obtain blood sample for pharmacokinetic (PK) analysis as soon as possible.^f Serum creatine phosphokinase (CPK) and lactate dehydrogenase (LDH). Fractionate bilirubin, if total bilirubin $\geq 2 \times \text{ULN}$. Obtain complete blood count with differential to assess eosinophilia. Record the appearance or worsening of clinical symptoms of liver injury (eg, fatigue, nausea, vomiting, right upper quadrant pain), or hypersensitivity, on the adverse event (AE) report form. Record use of concomitant medications (including acetaminophen, herbal remedies, and other over-the-counter medications) on the concomitant medications CRF. Record alcohol use on the liver event alcohol intake CRF. Exclude pregnancy. 
For bilirubin or INR criteria:
 
 Anti-nuclear antibody, anti-smooth muscle antibody, Type 1 anti-liver kidney microsomal antibodies, and quantitative total immunoglobulin G (IgG) or gamma globulins. Serum acetaminophen adduct high performance liquid chromatography (HPLC) assay (quantifies potential acetaminophen contribution to liver injury in participants with definite or likely acetaminophen use in the preceding week; James, 2009). 
NOTE: Not required in China.
 
 Liver imaging (ultrasound, magnetic resonance, or computerized tomography) and/or liver biopsy to evaluate liver disease; complete Liver Imaging and/or Liver Biopsy CRFs.

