#### 5.1.1.1.3 Study periods

The duration of the study for each study participant is approximately 38 weeks.; consisting of the following 3 periods:

- Screening Period (up to 28 days): Visit 1, Day -28 to Day -1
- Treatment Period (24 weeks) including Baseline visit: based on the first planned treatment starting from Visit 2 at Day 0 to the last planned treatment on Visit 15 at Day 168 (Week 24)
  - 400mg loading dose phase for doses at Week 0, Weeks 2 and 4 followed by 200mg Q2W maintenance dose phase thereafter (at Week 6, 8, 10, 12, 14, 16, 18, 20, 22 and 24)
  - PK profile treatment Period: Day 72±6 hours to Day 80±6 hours. These visits may be conducted at home visit.
- Safety Follow-Up: The end of study visit will be performed on 70 days after last IMP through SFU visit.

The end of the study is defined as the date of the last visit of the last study participant in the study. Study participants are considered to have completed the study if they complete the last scheduled study visit (Screening, Baseline Visit, Treatment Period [through Week 24], and SFU). The safety follow-up visit is 70 days post last dose. If study participants are continuing onto commercial Cimzia, the safety follow-up is 30 days post last dose.

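### SAP 5.2 defines a study completer by the safety follow-up visit alone, while Protocol 4.4 and SAP 5.1.1.1.3 also require the Treatment Period through Week 24

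*SAP*

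**What the plan says.** Three places define completion of the study.

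- Protocol 4.4: a completer "has completed all portions (Screening, Baseline Visit, Treatment Period [through Week 24], and SFU) of the study".
- SAP 5.1.1.1.3 carries the same list. Participants are complete if they "complete the last scheduled study visit (Screening, Baseline Visit, Treatment Period [through Week 24], and SFU").
- SAP 5.2, which specifies the disposition outputs, says that "the participant will be regarded as a completer if the safety-follow-up (Visit 16, 70 days after last IMP through SFU visit) visit was completed". It mentions neither Week 24 nor Visit 15.

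The Schedule of Activities (Protocol 1.3) labels the Visit 16 column as both SFU and Early Discontinuation Visit (EDV). It times that column at "70 days after last IMP", with a window of 7 days either way, and not at a fixed study day.

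Protocol 8.3.5, on withdrawal for pregnancy, shows that an early leaver can have both visits. It asks first for the EDV ("The participant should return for an Early Discontinuation Visit") and then says "An SFU Visit should be scheduled 70 days after the participant has discontinued her study medication".

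The SAP 5.2 table is also to show how many participants discontinued prematurely, with reasons.

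**The concern.** The section that produces the completer count uses a looser rule than the protocol, and looser than another section of the same SAP. A participant who leaves well before Week 24 but returns for the 70-day SFU meets the SAP 5.2 rule and fails the other two. The same person also belongs among the premature discontinuations, so two rows that should be mutually exclusive can overlap. A programmer cannot settle this from the SAP, which states both rules.

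One secondary objective is CZP exposure over up to 24 weeks, and readers use the completion rate as a first indication of how much of that period was observed. The SAP 5.2 rule can only raise that rate relative to the protocol's, and it raises it more the better the sites are at bringing early leavers back.

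**Working it through.** **Timeline.** Screening is up to 28 days, the Treatment Period runs to Day 168, and the SFU is 70 days after the last dose. 28 + 168 + 70 = 266 days, and 266 / 7 = 38.0 weeks. This reproduces the stated duration of about 38 weeks, which therefore describes someone who goes through all portions.

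**When the SFU falls for an early stopper.** Nominal SFU day = last-dose day + 70.

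| Last dose | SFU day | Relative to Week 24 (Day 168) |
|---|---|---|
| Week 0, Day 0 | 70 | before |
| Week 2, Day 14 | 84 | before |
| Week 6, Day 42 | 112 | before |
| Week 12, Day 84 | 154 | before |
| Week 14, Day 98 | 168 | same day |
| Week 22, Day 154 | 224 | after |
| Week 24, Day 168 | 238 | after |

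For every last dose up to Week 12, the nominal SFU comes before Week 24.

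**Classification of a participant who leaves the Treatment Period before Week 24.**

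- Attends the 70-day SFU: completer under SAP 5.2; non-completer under Protocol 4.4 and SAP 5.1.1.1.3.
- Attends only an EDV: non-completer under all three, because SAP 5.2 names the follow-up 70 days after the last dose.
- Attends neither: non-completer under all three.

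The rules therefore disagree only about early leavers who attend the SFU.

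**Size.** The plan enrols 30 and expects at least 25 to complete Visit 13 (Week 12). Assume that the other 5 leave early, that the 25 complete both Week 24 and the SFU, and that nobody is replaced. Let k of the 5 attend the SFU.

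- Protocol 4.4 and SAP 5.1.1.1.3: 25/30 = 83.3%, whatever k is.
- SAP 5.2: (25 + k)/30. With k = 0 this is 25/30 = 83.3%; with k = 5 it is 30/30 = 100%.
- Each early leaver who attends the SFU adds 1/30 = 3.3 percentage points.

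**The case against.** The strongest reply is that the SAP already holds the right definition. SAP 5.1.1.1.3 lists the Treatment Period through Week 24, and Change #2 in the SAP amendment log deliberately revised that section to include the list. The programmed table might follow it. This stands as far as it goes: the documents show that early leavers can be counted as completers, not that they will be. But SAP 5.2 is the section that specifies the table. None of the logged changes touches it, and SAP 6.2 declares no departure from the protocol's planned analyses.

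A second reply is that early stopping is visible elsewhere. SAP 5.2 also tabulates discontinuations with reasons and lists termination dates, and SAP 5.6.1 summarises injections, total doses and duration of exposure. That limits the harm, but it does not correct the completer count.

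A reader might also infer more than the documents support:

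- *That the shared Visit 16 column makes every EDV attendance a completion.* It does not. SAP 5.2 refers to the 70-day follow-up. Protocol 8.3.5 schedules the EDV and SFU separately, and SAP 5.1.1.1.2 and 5.1.1.1.4 treat the EDV as its own event. The shared label is untidy, but it is not the mechanism.
- *That antibody, safety or PK denominators are distorted.* They are not. They rest on the Safety Set, the PK Set, non-missing data or antibody category, never on completer status.
- *That anyone who stops CZP is a non-completer.* Protocol 4.4 defines completion by portions of the study, not by doses received. Appendix 6 provides, in the liver setting, to "permanently discontinue study medication and continue participant in the study for any protocol-specified follow-up assessments". Protocol 4.4 does not clearly exclude someone who stays off drug through Week 24 and the SFU.

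**Conclusion.** Wrong as written, and minor. SAP 5.2 omits the Week 24 condition that Protocol 4.4 and SAP 5.1.1.1.3 both require. Read literally, it can place an early leaver in the completed and prematurely discontinued rows at once.

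The gap of up to 16.7 percentage points (100% against 83.3%) is the worst case of an illustration, not a forecast. The plan's figure of 25 concerns Visit 13 only, so it does not imply that 25 will reach Week 24. Replacing withdrawn participants, which the plan allows, would change the denominator. The finding that holds without these assumptions is the classification itself: the SAP 5.2 count exceeds the protocol count by exactly the number of early leavers who attend the SFU. The consequence stops at disposition reporting.

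**What to change.** Replace the SAP 5.2 sentence with: 'A study completer is a participant who completed the Treatment Period through Week 24 (Visit 15) and the SFU Visit.' This matches Protocol 4.4 and SAP 5.1.1.1.3. Add that attending the SFU or an EDV without completing the Treatment Period through Week 24 does not make a participant a completer. Word the addition in terms of the Treatment Period and not of dosing, so that it does not exclude someone who stops CZP but remains in the study through Week 24 and the SFU.

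Optionally, report completion of study medication in a separate row, using dosing data already collected.

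The cost is a short SAP edit and at most one extra table row. The downside is that the reported completion rate may be lower.

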### 5.3 Primary Endpoint(s) Analysis

The primary endpoint analysis is to evaluate the PK of CZP (utilizing the ECLIA method) in adults with active RA.

Pharmacokinetics will be assessed using the PKS.

#### 5.3.1 Definition of endpoint(s)

The primary PK variables will include the following PK parameters ( $C_{min}$  and  $AUC_{0-\tau}$ ) following 10 weeks of CZP dosing.

- $AUC_{0-\tau}$ : area under the curve over a dosing interval
- $C_{min}$ : Minimum plasma drug concentration during a dosage interval

#### 5.3.2 Main analytical approach

The primary PK parameters in plasma are:  $C_{min}$  and  $AUC_{0-\tau}$ .

The primary PK parameters of CZP will be summarized by MTX use at screening using descriptive statistics (number of available observations ( $n$ ), arithmetic mean, median, SD, minimum, maximum, geometric mean, geometric CV and 95% CI for the geometric mean (assuming lognormally distributed data)). Values below the LLOQ will be reported with a clear sign indicating that they were below the LLOQ.

For calculation of the PK data (including parameter), the actual blood sampling times will be used.

All PK data will be listed and summarized for all study participants for the PKS including  $n$ , arithmetic mean, median, SD, minimum, maximum, geometric mean, geoCV and 95% CI for the geometric mean.

The following rules will apply for the PK data summaries:

- PK parameters are reported with 3 significant digits and Descriptive statistics reported to 4 significant figures for the mean, median and standard deviation (SD) and to 3 significant figures for all others.
- Values below the LLOQ will be reported as BLQ for individual data and will be substituted with  $LLOQ/2$  for the descriptive statistics
- Descriptive statistics of PK concentrations will be calculated only if at least  $\frac{2}{3}$  of the individual data at a specific sampling timepoint are measured and are quantifiable (ie, above LLOQ) and if  $n \geq 4$ . If  $n < 3$ , then only  $n$ , minimum and maximum will be presented and if  $n = 3$ , then only  $n$ , median, minimum and maximum will be presented and the other descriptive statistics will be left blank.
- Descriptive statistics of PK parameters will be calculated only if at least  $\frac{2}{3}$  of the individual data are calculable and if  $n \geq 4$ . If  $n < 3$ , then only  $n$ , minimum and maximum will be presented and if  $n = 3$ , then only  $n$ , median, minimum and maximum will be presented and the other descriptive statistics will be left blank.

- If no study participants have data, only n=0 will be presented.
- The 95% lower and upper CI should be left blank if the SD (or equivalently the geoCV) is equal to 0
- The geoCV will be calculated using the following formula where SD is the standard deviation of the log-transformed values:  $\text{geoCV} (\%) = \sqrt{(\exp(\text{SD}^2) - 1)} \times 100$

### 5.3.2.1 Handling of dropouts or missing data

Measurements that are BLQ will be imputed with half of the LLOQ for the purpose of calculating the geoMean and its 95% CI, the geoCV, the arithmetic mean, and SD for summaries and figures. If any summary value (geoMean, arithmetic mean, lower CI level or minimum) is lower than LLOQ, then 'BLQ' will be displayed.

For the individual figures, any concentrations that are BLQ will be regarded as missing, with the exception of predose measurements BLQ on Day 0, which will be imputed with zero for linear scale plots.

### 5.3.3 Sensitivity analysis

Not applicable.

### 5.3.4 Supplementary analyses

Not applicable.

## 5.4 Secondary Endpoint(s) Analysis

The secondary objective is to evaluate CZP exposure over a maximum of 24 weeks administration to adults with active RA and evaluate the safety of CZP in adults with active RA.

### 5.4.1 Key secondary endpoint(s)

The secondary variables will include the following endpoints.

- CZP plasma concentrations over duration of the study including Visit 2 till Visit 16 (70 Days through SFU visit).
- Treatment-emergent SAEs from first dose through the SFU Visit.
- Treatment-emergent AEs leading to withdrawal from first dose through the SFU Visit

